1. SUMMARY

To achieve global goals for the treatment of HIV, most high-prevalence countries are experimenting with and scaling up differentiated service delivery models (DSD). A handful of efforts have been formally described and evaluated in the literature; many others are being implemented formally or informally under routine care, without a research or evaluation goal. For most countries, however, we have little evidence on the big picture—the proportion of clinics offering alternative models, eligibility criteria and the proportion of patients considered eligible, the number of patients actually participating, health outcomes such as viral suppression, empirical resource utilization compared to traditional care, variations among the models, duration of patient participation, fidelity to model guidelines, effects on clinic efficiency, and sustainability without external donor support.

AMBIT a set of data synthesis, data collection, and data analysis activities aimed at generating information for near- and long-term decision making and creating an approach and platform for ongoing evaluation of differentiated models of HIV treatment delivery in the future. The project will collect and analyze a wide range of existing data sets pertinent to DSD. This protocol is for an analysis of existing medical record data collected by the Ministry of Health (MOH), implementing partners, and other completed, ongoing, or new evaluations, trials, and observational studies. Outcomes to be reported include coverage/uptake of DSD, patients' outcomes, and distribution of each model. There will be no study interaction with individual patients, providers, caregivers, or others for this analysis.

3. BACKGROUND, RATIONALE, AND OBJECTIVE

[figure not shown]
a. Background

To achieve global goals for the treatment of HIV, most high-prevalence countries are experimenting with and scaling up differentiated service delivery models (DSD). To date most of these efforts have focused on "stable" antiretroviral therapy (ART) patients, who have passed the period of high mortality and loss-to-follow-up immediately after initiating ART. Stable patients are believed to require fewer provider resources (e.g. clinical consultations) and are able to benefit from community-based service delivery that is closer to home[1] and from less intensive clinic visits. A handful of efforts have been formally described and evaluated in the literature[2–6]; many others are being implemented formally or informally under routine care, without a research or evaluation goal. While there is currently no reliable count of how many ART patients are participating in alternative service delivery approaches, it is likely that nearly every major HIV treatment partner supported by PEPFAR and the Global Fund have introduced one or more alternative models of care into the programs they support.

At present, some studies have reported outcomes for specific models of care and/or compared one model to another, and several large studies are currently underway to evaluate individual models. For most countries, though, we have little evidence on overall impact. We cannot currently estimate basic aggregate descriptive measures such as the proportion of clinics offering alternative models, the proportion of patients considered eligible or the number of patients actually participating. Nor do we know eligibility criteria for each model in each country, empirical resource utilization compared to traditional care, or core outcomes such as viral suppression. We have almost no data on variations among the models, duration of patient participation, fidelity to model guidelines, effects on clinic efficiency, and sustainability without external donor support. Many efforts are underway to improve use of alternative models, but their focus is on implementation rather than high-level evaluation or analysis of the phenomenon as a whole.

For purposes of this protocol, we will refer to any approach to service delivery that is tailored to some aspect of patient needs as a "differentiated service delivery model," or DSD. The original model of clinic-

based ART provision for all patients will be called the "conventional" model and will be considered a single model of care. All other models of care will collective be called "alternative" models. A health system that optimizes the provision of approaches will offer one or more alternative models of care for all ART patient populations,

stratified on the basis of criteria ranging from setting (e.g. rural v urban) to risk factors (MSM v young women), patient characteristics (age, sex, condition), to clinic capacity. In this taxonomy, the conventional model of care may serve a specific group of patients—those who require additional services—and it is thus a differentiated model in itself.

In Malawi, the Ministry of Health (MOH) and its implementing partners are currently supporting the scale-up of several alternative models of care ART patients who are stable on ART. These include amongst others, multi month dispensing, fast track refills, nurse led community ART and adolescent centric treatment groups. While some specific DSD models have been or are being evaluated[7-10], there has not yet been an assessment of the reach or impact of DSD at national scale.

b. Rationale

In the published literature and conference presentations, calls for funding proposals, and MOH documents, DSD are assumed to generate a wide range of potential benefits. These include better access to and outcomes of treatment, increased clinic capacity and lower costs for providers, lower costs for patients, and better quality and greater satisfaction for both providers and patients. Despite a high level of confidence on the part of DSD advocates, ministries of health, funders, and implementing partners that at least some of these benefits must materialize, there is in fact very little evidence to support these assumptions. Published research to date has suggested modest or minimal improvement in health outcomes and small reductions (if any) in per-patient provider costs. We note that there is little room for short-term improvement in health outcomes, as most patients enrolled in alternative models to date have been virally suppressed at entry, but DSD may certainly affect long-term retention in care. We also expect only modest potential for per-patient out-of-pocket cost reductions, due in part to the large share of costs attributable to medications[11-13]. We have found no published evidence that moving HIV patients into alternative models increases the quality or quantity of services that clinics provide to conventional-model patients or patients with non-HIV conditions.

Fortunately, in the past half-decade, substantial groundwork has been laid for standardizing methods for evaluating the performance of DSD at the patient level. We are thus at a point in time at which many alternative models are already being implemented and some evaluated, and an initial set of evaluation indicators has been published[14]. With some micro-data in hand, but little "macro" evidence of overall scale, impact, costs, and benefits, this is therefore an apt time to launch a big picture analysis of DSD, to help guide ministries of health, donor agencies, and others to make better decisions about what to scale up, where, and for whom.

c. Objective

The objective of this study is to analyze existing data sets with data relevant to differentiated service delivery for HIV treatment in Zambia, Malawi, and South Africa. This protocol is solely for the analysis of existing data; the study contains no interaction with patients, providers, or other individuals.

The specific aims of the study are to assess the current extent of DSD implementation and uptake under current guidelines and to evaluate outcomes, costs, and benefits of DSDs.

The AMBIT project has three focus countries, South Africa, Zambia, and Malawi. This protocol is specifically for data collected in Malawi. Protocols specific to Zambia and South Africa will be submitted separately to the appropriate governmental and institutional review boards.

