Outcomes 9-11 measure health outcomes by model of care. For these outcomes, we will begin with descriptive analyses of the characteristics of the population stratified by model of care. For each outcome described above, we will conduct a crude analysis comparing the proportion of subjects with the outcome by model of care. Next, we will conduct an analysis for each outcome accounting only for clustering using generalized estimating equations (GEE) with an unstructured correlation matrix and clustering by treatment site. In all cases the outcomes are dichotomous and therefore we will calculate risk differences comparing the intervention to the comparison arms using a linear link function and a binomial distribution. Next, should any imbalances between models of care be detected, we will adjust for those covariates in our GEE model. Finally, we will look for differences in the effects of the models of care by important baseline characteristics (e.g. size of the treatment population, rural vs. urban, province, etc.) using stratified analyses.

d. Dissemination of Findings

The results of this study will be disseminated as widely as possible in the study countries and globally. A full report will be made to local stakeholders and will be circulated widely and posted on our website. We will also develop a short briefing document to send to the Ministry of Health, donor agencies, and other interested organizations, and we will present the results at relevant conferences domestically and internationally. One or more journal manuscripts will be submitted to an appropriate peer-reviewed international journal.

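### Outcomes 9–11 appear to compare alternative models with one undivided conventional group, and clustering by site does not by itself remove differences between clinics that do and do not offer those models

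*Protocol*

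**What the plan says.** Section 3a sets the taxonomy. Conventional care "will be considered a single model of care", and everything else is grouped as alternative ("All other models of care will collective be called" that). The same section adds that "the conventional model of care may serve a specific group of patients", namely those with additional needs. It also lists "the proportion of clinics offering alternative models" among the quantities that cannot yet be estimated, so the authors recognise that clinics differ in what they offer.

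Section 5b includes all patients aged 15 or over in HIV care anywhere in Malawi.

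Section 7c sets the analysis of Outcomes 9–11:

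- First, "we will conduct a crude analysis comparing the proportion of subjects with the outcome by model of care".
- Then a GEE with unstructured correlation and the treatment site as cluster, giving risk differences.
- Then, "should any imbalances between models of care be detected, we will adjust for those covariates in our GEE model".
- Finally, stratified analyses by clinic features such as size, rural or urban setting and province, to look for differences in effect.

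The comparison arm is not defined further. Whether the clinic offers the alternative model is not named at any step.

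Section 3b raises effects on patients who stay in conventional care, as an evidence gap: "We have found no published evidence that moving HIV patients into alternative models increases the quality or quantity of services that clinics provide" to them.

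**The concern.** A patient can be in an alternative model only where a clinic offers one. Conventional patients come both from those clinics and from clinics that offer none. If the two kinds of clinic differ in retention or suppression for any other reason, part of that difference enters the risk difference as though the model had caused it. Restricting to eligible or stable patients would not remove it, because it is a property of the clinic.

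The stakes are set by the protocol's own expectations. Section 3b expects small health gains at most, so an error of one to three points could be as large as the effect sought. Section 7a foresees up to 1,000,000 records, so a biased estimate could carry a narrow interval. The results are meant to inform which models to scale up and where.

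**Working it through.** The protocol gives no effect size, clinic gap, availability or uptake, so there is no planned figure to reproduce. Every numerical input below is an assumption.

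**Crude contrast.** Let p be the share of patients at offering clinics, u the uptake of the alternative model there, g the outcome gap between offering and non-offering clinics, e the true model effect, and k any spillover to conventional patients at offering clinics. The share of conventional patients who sit at non-offering clinics is

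w = (1 − p) / [(1 − p) + p(1 − u)].

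The pooled risk difference is then e + w·g − (1 − w)·k. With e = 0 and k = 0 the bias is w·g. For g = 5 points:

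- p = 0.5, u = 0.5: w = 0.50/0.75 = 0.667, bias 3.3. Direct check with 90% v 85% retention: 90 − (0.25×90 + 0.50×85)/0.75 = 90 − 86.7 = 3.3.
- p = 0.9, u = 0.3: w = 0.10/(0.10 + 0.63) = 0.137, bias 0.7.
- p = 0.3, u = 0.7: w = 0.70/(0.70 + 0.09) = 0.886, bias 4.4.

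Over p from 0.3 to 0.9 and u from 0.3 to 0.7, the bias is 0.3–1.8 points for a 2-point gap, 0.7–4.4 for 5 points and 1.4–8.9 for 10 points. A gap in the other direction reverses the sign.

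**GEE step.** Simulation: 200 sites, half offering, 50% uptake, baseline 85%, site SD 4 points, 300 runs, identity link with a constant-variance approximation, e = 0, k = 0, g = 5 points. Mean risk difference in points:

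| Patients per site | Independence | Exchangeable | Within-site |
|---|---|---|---|
| 20 | 3.2 | 2.5 | −0.1 |
| 50 | 3.2 | 1.9 | −0.1 |
| 200 | 3.3 | 0.9 | 0.0 |
| 1,000 | 3.3 | 0.2 | 0.0 |

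The remaining bias therefore depends on the working correlation and on site size. The planned unstructured matrix was not simulated. Treated as free correlations between patients in a site, it needs m(m − 1)/2 parameters: 19,900 at 200 patients and 499,500 at 1,000. The weighting that would actually be used cannot be told from the text.

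**Spillover.** With g = 0, e = 3 and k = 3, the simulation gives about 2.0 under independence (formula: 3 − 3/3 = 2), 1.7 down to 0.2 under exchangeable as site size rises from 20 to 1,000, and about 0 within sites. With e = 0 and k = 3 it gives about −1.0, −1.3 to −2.8, and −3.0.

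**What each separated contrast estimates**, leaving patient selection aside:

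- Alternative v conventional at the same clinics: e − k.
- Alternative v conventional at non-offering clinics: e + g.
- Conventional at offering v non-offering clinics: g + k.

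The first equals the second minus the third, so three unknowns rest on two independent contrasts. No single contrast isolates e without an assumption about g or k.

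**The case against.** The strongest reply is that section 3a is taxonomy, not a comparator specification. It counts conventional care as one model beside several alternatives and does not say that patients are pooled across clinics. A reader might infer that the protocol states this pooling; it does not. It is the natural reading of sections 3a, 5b and 7c together, and a separate analysis plan could still divide the group. What stands is that section 7c already fixes the cluster, correlation, link and distribution and leaves this out.

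Other tempting readings also go too far:

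- **That offering clinics are better supported, so the bias favours alternative models.** Section 3a says only that nearly every major partner has probably introduced some model. That suggests wide availability, which shrinks w, and gives no direction for the gap.
- **That the GEE leaves the whole gap in place.** With exchangeable correlation and large sites, most of it goes.
- **That clinic information is absent.** Section 6b plans aggregate clinic-level data on resources, providers and volumes, and section 7c plans adjustment and stratification. But adjustment depends on detecting an imbalance, its covariates are unnamed, and stratification serves to look for effect differences. None names offering status.
- **That spillover is an established effect, or that the plan makes it impossible to study.** Section 3b reports a lack of evidence, and nothing forbids dividing conventional patients by site.
- **That a within-clinic comparison settles the matter.** It does not remove spillover. Since section 3a suggests that those left in conventional care may be the patients with greater needs, it is also more exposed to patient selection.

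**Conclusion.** The point holds in limited form. Followed as naturally read, the analysis of Outcomes 9–11 does not separate within-clinic from between-clinic differences, and clustering by site is not a substitute for doing so. For an assumed 5-point clinic gap and no true effect, the crude bias is about 0.7 to 4.4 points. The GEE bias is about 3.2 points under independence, falling to 0.2 under exchangeable correlation with 1,000 patients per site. These sizes rest on assumed gap, availability, uptake and site variation. The structural point needs only that offering and non-offering clinics differ in outcome. This is a low-cost improvement to the analysis text; the documents do not show that the planned results would be wrong by any particular amount.

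**What to change.** In section 7c, for Outcomes 9–11, classify each conventional patient by whether the clinic offered the alternative model at that time. Derive this from the model-enrolment and duration fields in section 6b and the facility coverage calculated for Outcome 8, where these allow. Report side by side:

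1. Alternative v conventional at the same offering clinics, stratified by or conditioned on site, with adjustment for patient eligibility and stability.
2. Alternative v conventional at non-offering clinics.
3. Conventional at offering v non-offering clinics.

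State that (1) removes clinic differences but not spillover and is more exposed to patient selection, that (2) stays open to clinic differences, and that (3) mixes clinic differences, selection and spillover. The 2014 pre-DSD period in section 6a can serve as a reference for the clinic gap, if that gap is assumed stable over time. Making (1) the only headline result would be a debatable trade-off and is not needed.

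Cost: analysis work and wording. Clinics with only one kind of care drop out of (1), with some loss of precision. Offering dates may be incomplete, because section 6a notes that the national electronic system does not fully record model of care.

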4. OVERVIEW OF STUDY DESIGN

To achieve the study aims, we will analyze pre-existing data sets that contain information relevant to DSD at national and sub-national levels. All adult patients seeking care for HIV in the country during the study period will be eligible to be included in the study through use of their clinical record data. There will be no direct interaction with study subjects. Data will be collected from existing patient records, including clinic files, registers, and databases. We will find, access, and then synthesize existing data from as many sources as we can identify.

Prior to starting data collection for this evaluation, we will develop descriptions of the available data sources and the models of care reflected in the data sets. We will then collect primary data from the Ministry of Health, treatment support partners, researchers, and funders, as described below. Finally, we will analyze individual and pooled data sets to generate as much information as possible about the uptake, utilization, outcomes, benefits, and costs of different models of care.

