5. STUDY SITES AND POPULATION

a. Study Sites

The evaluation will be conducted nationally in Malawi. Data collected may pertain to the entire national cohort of ART patients (e.g. Baobab Health NART) or to specific smaller cohorts developed by implementing partners, other researchers, and clinics themselves.

b. Inclusion Criteria

This study aims to measure coverage and outcomes of DSD across Malawi. For this reason, we will include in our study all adults who are accessing care for HIV anywhere in the country. The inclusion criteria are shown below.

Inclusion criteria

- ≥ 15 years old
- Patients accessing care for HIV within the data collection period (January 1, 2014 to February 28, 2021)
- In any HIV transmission risk group (general adults and adolescents, high transmission risk populations)

Exclusion criteria

None

Children younger than 15 are excluded from this study for two reasons. First, they are typically treated in pediatric HIV programs that have different drug regimens, visit schedules, and models of care than do adults. Second, the vast majority of DSD implementation in the focus countries to date has involved only adult and adolescent patients, not children [15].

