6. DATA SOURCES AND MANAGEMENT

a. Data Sources

The MOH and its partners will implement the DSD strategies addressed in this study. This protocol is solely for an evaluation of the coverage and outcomes of the interventions. The study team will have no involvement in providing services nor any interaction with patients. The evaluation will instead rely solely on existing, retrospective national-, facility-, and patient-level records.

Routine data sources to be accessed for this study include:

- Baobab Health National ART (NART) System
- Baobab Health Laboratory Information Management Systems (LIMS)
- Other MOH electronic and paper patient records and registers which capture relevant information related to the care and treatment of patients in any model of ART care and treatment. NART does not currently fully capture model of service delivery, for example, so access to paper files at clinics may be required to build the study database.
- Existing, de-identified data sets from trial, cohort, and observational studies, in collaboration with implementers, technical support partners, and research organizations.

The Ministry of Health will be asked to assure and facilitate access to Baobab Health's NART, LIMS and other routinely collected sources of electronic data.

Data will be collected for all patients in each data set who accessed care for HIV on or after January 1, 2014. The focus countries began large-scale implementation of DSD in 2015 or 2016. Starting in 2014

will thus allow us a pre-intervention period for comparison. Data collection will continue throughout the study period, which ends on February 28, 2021.

b. Data Fields to be Collected

Below (Table 1) we summarize the existing data required for the evaluation. A detailed list of data fields follows this summary.

Table 1. Data sought for evaluation of DSD

Themes	Potential availability and source(s)
Proportion of current ART patients meeting definition	Data from electronic medical records, existing M&E reports, IeDEA
of stable; distribution of reasons for not meeting	and PEPFAR partners, cohorts under observation, facilities
definition	participating in others' studies
Geographic distribution and description of	Reports from existing implementers and technical support
differentiated models in use	partners and MOH
Number (proportion) of patients in each model at time	Data from existing implementers and technical support partners,

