of data collection; patient-months enrolled in each	with quality assessment through primary data collection at a
model in previous 12-month period	sample of sites
Location, duration, and frequency of dispensing for	Electronic medical record data; pharmacy data
ARVs and other ART-related medications (e.g. INH)	
Number of facility and non-facility visits per patient	Electronic medical record data
per year, by model of care and purpose of visit (e.g.	
clinical consultation, medication pickup)	
Number and outcomes of viral load tests, CD4 counts,	Electronic medical record data
and other ART-related laboratory assays per patient	
per year, by model of care	

The specific data fields available and required for different patient types will vary slightly (e.g. viral loads will not be available for patients newly initiating treatment). In general, however, we will collect a common set of variables for all patients. The specific fields are listed below:

Demographic information

- Electronic medical record system number (e.g. Baobab Health NART record number)*
- Clinic file, register, and card numbers (assigned by the clinic)*
- National ID number*
- Name*
- Date of birth*
- Weight and height or BMI
- Sex
- Age in years
- Marital status if recorded
- Employment status if recorded
- Education level if recorded

· Smoking and alcohol use if recorded

*Identifiers like name and date of birth are required to link electronic and paper-based records pertaining to individual patients. Many clinics use name or initials and date of birth to create a clinic record number. For example, numbers and dates of clinic visits can typically be extracted from Baobab Health, but the specific model of care used by an individual patient may require linking Baobab Health records to data manually transcribed from paper clinic records.

Clinical information

- Date of positive HIV test (if available)
- Dates of all clinic visits (including pre-ART and after ART initiation)
- Primary purpose of all clinic visits (e.g. HIV test, CD4 count, counselling, ARV dispensing, ART monitoring, etc.)
- Dates of next scheduled clinic visits (dates patients are expected to return to clinic)
- Date treatment eligibility determined, if reported
- Date and result of CD4 count indicating treatment eligibility (baseline)
- WHO stage and clinical conditions
- Date and result of TB symptom screen
- Date, type, and result of TB test
- Date TB treatment initiated, if relevant

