7. DATA ANALYSIS

a. Sample Size

In order to measure national coverage of DSD, we will access data for up to the entire national ART cohort. In Malawi, the estimated number of individuals on ART is currently 740,000 [16]. This is expected to increase to \geq 90% of the entire HIV-infected population by the time the study ends. We therefore expect to collect and analyze data for up to 1,000,000 individuals, the estimated HIV-positive population in Malawi [16]. As noted above, all data will be drawn from records that exist at the time of data collection; the study will have no interaction with study subjects.

b. Outcomes

To estimate uptake, benefits, and costs of DSD, we will aim to report the following results, stratified by model care and/or other patient or clinic/model characteristics:

- Percentage of current ART patients eligible for any alternative model, under current guidelines
- 2. Demographic, economic, and clinical characteristics of patients in each model, as data allow.
- 3. Patient-months enrolled in any DSD and in each model
- 4. Frequency of transfer between models of care, including back to the conventional model
- 5. Location, duration, and frequency of ARV dispensing
- 6. Number of clinical visits/patient/year
- 7. Quantities of resources used/patient/year
- 8. Geographic distribution of patients enrolled in each DSD
- 9. Retention on ART, measured at 6-month intervals
- 10. Proportion virally suppressed (< 400 copies/ml³)
- 11. Other outcomes relevant to DSD that can be estimated from available data

Note: as this is not a clinical trial, we have not designated primary and secondary outcomes. We will report as many of the above outcomes as data allow.

c. Analysis

To evaluate the broad, national- or system-wide implications of differentiated models of ART delivery in the context of health systems in sub-Saharan Africa, we will conduct the following analyses.

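### The national coverage figure for differentiated service delivery is not secured as national: model of care is incompletely recorded, and nothing ties the data that will be found back to the whole ART population

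*Protocol*

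**What the plan says.** The target is national. Protocol section 5b states: "This study aims to measure coverage and outcomes of DSD across Malawi". Section 7a justifies the size of the data set in the same terms: "In order to measure national coverage of DSD, we will access data for up to the entire national ART cohort".

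The data are opportunistic. Section 4 says the team will "synthesize existing data from as many sources as we can identify". Section 5a allows the data to cover the national cohort, with NART as the example, "or to specific smaller cohorts developed by implementing partners, other researchers, and clinics themselves".

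Model of care, which is the numerator of coverage, is the weak field. Section 6a says: "NART does not currently fully capture model of service delivery, for example, so access to paper files at clinics may be required". Section 6b describes linking electronic records to data transcribed from paper. For the number of patients in each model, Table 1 names implementing and support partners as the source, "with quality assessment through primary data collection at a" sample of sites whose selection is not described.

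In section 7c, outcomes 1-4 are reported as proportions of the patients in the sample. Outcome 8 is a ratio for each facility, DSD enrolees over current ART patients, taken either from national patient-level indicators or from partner aggregates, and then mapped.

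**The concern.** Access to every ART record would supply the denominator of coverage but not a complete numerator. The numerator depends on which partners share data, which clinics have paper files abstracted, and which patients have a model recorded. Partners who run alternative models may well hold data from sites that are not typical.

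The stated steps contain no link from the patients with a known model to the national ART population: no frame of sites, no weighting, no treatment of patients whose model is unknown, and no sentence limiting the inference to contributing sites. Followed as written, they allow a proportion from partner sites to be presented as national coverage. Section 8d says the findings should help the ministry target its interventions and project budgets, so the distinction matters to the user. The very large number of records makes the figure look more certain than it is.

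**Working it through.** **1. The plan's own figures.** Section 7a gives 740,000 people on ART and a ceiling of 1,000,000, the estimated number living with HIV. 740,000 / 1,000,000 = 74%. The expected rise to at least 90% gives 0.90 × 1,000,000 = 900,000, which fits under the ceiling. These are population counts, not a sample-size calculation, and nothing in them is wrong. They do not say for how many people the model of care will be known.

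**2. Set-up.** Let f be the share of current ART patients with a known model, p the DSD coverage among them, and u the coverage among the rest. National coverage is

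C = f·p + (1 − f)·u.

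The documents give none of f, p or u, so the values below are assumptions.

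**3. Worst-case bounds.** As u runs from 0 to 1, C runs from f·p to f·p + (1 − f). The width is 1 − f, whatever p is and however many records there are. For comparison, the last column gives the simple binomial 95% half-width, 1.96·√[p(1 − p)/n], with n = 740,000·f. All rows assume p = 50%.

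| Assumed f | Records with known model | Bounds on C | Width (points) | Sampling half-width (points) |
|---|---|---|---|---|
| 0.95 | 703,000 | 47.5% to 52.5% | 5 | 0.12 |
| 0.80 | 592,000 | 40% to 60% | 20 | 0.13 |
| 0.60 | 444,000 | 30% to 70% | 40 | 0.15 |
| 0.40 | 296,000 | 20% to 80% | 60 | 0.18 |

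Changing p moves the bounds but not their width. At f = 0.80, p = 30% gives 24% to 44%, and p = 70% gives 56% to 76%. A site-clustered interval would be wider than the binomial one, but it would still say nothing about the patients whose model is unknown.

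**4. Direction.** Reporting p as national is in error by p − C = (1 − f)(p − u).

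- With f = 0.80, p = 50% and u = 25%: 0.20 × 25 = 5 points too high.
- With u = 75% instead: 5 points too low.
- At f = 0.40 the same two cases give 15 points too high and 15 points too low.

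If patients with no recorded model are counted as conventional care, the reported figure is f·p and the error is −(1 − f)·u. With f = 0.80 and u = 50% that is 10 points too low. The sign therefore depends on who is unrecorded and on how they are counted. The documents settle neither.

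**The case against.** Several points on the other side stand.

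- **NART is not shown to be the only national source.** Section 5a introduces it as an example, section 6a also lists the laboratory system and other ministry records, and section 7c speaks of national sources in the plural. What can be said is that no other source is named for the whole cohort and none is stated to record model of care.
- **A remedy is described.** If paper-file linkage were completed at every site, the problem would largely go away. The protocol says only that such access may be needed, and commits to no set of clinics.
- **Facility-level coverage is not itself biased by sites that do not contribute.** For outcome 8, a ratio at a contributing site describes that site. The problem arises when such ratios or pooled proportions are read as the country.
- **No confidence interval is prescribed for coverage in outcome 8.** One cannot say that the plan will publish a misleadingly narrow one. The comparison above shows only that sample size does not help.
- **The plan is silent on weighting.** It does not prescribe a single unweighted national percentage, and silence alone could be left to an SAP.

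That last point does not dispose of the matter. A national target, opportunistic sources and an admitted gap in the numerator are all stated in the protocol. If clinics are chosen for abstraction without a known selection probability, later weighting cannot fully recover it.

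**Conclusion.** The protocol states a national target, but its data route does not secure a national estimate. The uncertainty is governed by 1 − f: 5 points if model is known for 95% of ART patients, 20 points at 80%, 60 points at 40%. These shares are assumptions, because the documents do not report completeness.

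A reader might go further and conclude that the result will represent contributing sites and not Malawi, or that it will overstate coverage because those sites are the most active. The documents support neither as fact. Incomplete capture could be missing patients within sites rather than missing sites, and the error could run either way. No figure in the protocol is shown to be wrong. The point is a design weakness that should be corrected before any national percentage is reported.

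**What to change.** For any coverage figure described as national:

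1. Estimate coverage within site or stratum (district, facility size, urban or rural, supporting partner) and weight to the count of current ART patients in the national system: Σ N_h·p_h / Σ N_h, with a site-clustered 95% CI.
2. Report the share of national ART patients whose model is known, overall and by stratum.
3. Show bounds from f·p to f·p + (1 − f) for those with unknown model, and do not count them as conventional care by default. Weighting cannot supply coverage for a stratum with no contributing site, so that stratum belongs in the bounds.
4. Label unweighted or pooled proportions as applying to contributing sites.
5. Where clinics are picked for paper-file abstraction or for the Table 1 quality check, choose them at random within strata where access allows, and record where it did not.

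The cost is an added weighting step, a wider and more honest interval, and some selected sites that are harder to reach. The first step needs usable national counts of current ART patients by site or stratum, which the protocol does not document and the team should confirm. The share with known model, the bounds and the labelling need little beyond the data already planned.
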